In case of early discontinuation, after the EDV, or for subjects who complete the study but do not continue BRV treatment, the Down-Titration Period starts with scheduled Down-Titration Visits (DTV). Dose will be down titrated by a maximum of half the dose every week for a maximum of 4 weeks until a dose of 1mg/kg/day is reached.

After 2 weeks free of study drug, the Safety Period, subjects will complete the Safety Visit (SV).

The study is defined to be completed if the study status on the study termination form is marked as completed. This indicates that all planned visits have taken place. Planned visits are dependent on whether a subject discontinues the study or not, and on whether a subject goes into another study or takes marketed drug after FV.

At each visit, the subject/parent(s)/legal representative(s) will receive a DRC, which has to be filled in daily by parent(s)/legal representative(s) or subject, if applicable, and returned at the next visit. No DRC will be dispensed at the SV or the FV.

The date and the number of epileptic seizures will be recorded on the DRC, as well as the type of seizure (according to individual description of seizures), occurrence of clusters, intake of concomitant AEDs, undesirable events with start and end dates, health care provider consultations not foreseen per protocol, and changes in concomitant medication, if applicable.

The written information will be discussed with the subject/parent(s)/legal representative(s) at each visit in order to ensure completeness and accuracy. As a result of the discussion, the Investigator will assess the seizures according to the International League Against Epilepsy (ILAE) codes and record the seizure types and frequency on the electronic case report form (eCRF); he/she will also confirm the presence of AEs (if applicable). Concomitant medication changes, health care provider consultations not foreseen per protocol, and AEs will be reported by the Investigator on the specific pages of the eCRF.

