3.2.3 Study periods

[Table 3–1](#) shows which study periods are applicable to DE and LTFU subjects:

This document cannot be used to support any marketing authorization application and any extensions or variations thereof.
PUBLIC COPY

Table 3-1: Study periods

Period		Screening Period	Up-Titration Period			Evaluation Period							Down-Titration Period	Safety Period		
Subjects	Visit	ScrV	TV1	TV2	TV2	EV	MEV	FEV	MEV	FEV	MEV	YEV	...	FV/EDV	DTV	SV
			V1	V2	V3	V4	V5	V6	V7	...						
Subjects	DE	x	x	x	x	x	x	x	x	x	x	x	x	x	(x)	(x)
	LTFU					x	x	x	x	x	x	x	x	x	(x)	(x)
	Early Discontinuations												x	x	x	x

(x) – only applicable if the subject does not switch to another BRV study or is taking marketed drug after FV

The study is divided into 5 periods: Screening Period, Up-Titration Period, Evaluation Period, Down-Titration Period, and the Safety Period.

There is a Screening Period for all DE subjects. For DE subjects, this comprises assessments performed prior to the first dose of BRV in N01266. So start date of Screening Period is date of written informed consent and end date is the day before first dose of BRV (TV1-1). Although, patients in LTFU studies will not attend a screening visit, the screening information comprises information collected at various assessments during the core study and consequently will have been collected at different times depending on the domain. Domain specific information is detailed in Section 3.3.

The Up-Titration Period is only applicable to DE subjects, and the start date is the date of the first dose of BRV. The following algorithm is used to determine the end date:

- If the subject enters the Evaluation Period, the date 1 day prior to the EV is the end date
- If the subject does not enter Evaluation Period, the Up-Titration Period ends on the date of the final dose of BRV

For the Evaluation Period, the start date is the date of the first dose of BRV on or after the EV date, and the following algorithm is used to determine the end date:

- If the subject continues the study until it ends, the Evaluation Period ends on the date of FV
- If the subject prematurely discontinues the study, the date of EDV is the end date

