A discontinued subject or a subject who completes the study but does not continue BRV treatment will be considered entering the Down-Titration Period only if the subject has a record of at least 1 dose of BRV after the date of EDV. The start date of the Down-Titration Period is set as 1 day after the date of EDV, and the Down-Titration Period ends on the date of the final dose of BRV (DTV).

A discontinued subject without any dosing of BRV after the EDV will not have participated in the Down-Titration Period, and no artificial Down-Titration Period will be created for the purpose of analysis.

A discontinued subject is considered to have entered the Safety Period if the subject has at least 1 contact (scheduled visit, unscheduled visit (UV), or telephone contact) after the date of the final dose (DTV). The Safety Period starts 1 day after the date of the final dose of BRV irrespective of entering the Down-Titration Period, and end date is the date of last contact with the subject.

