8.1 Extent of exposure

The Evaluation Period BRV exposure duration (in months) will be calculated as the date of the final dose of BRV during the Evaluation Period minus the date of the first dose of BRV in the Evaluation Period plus 1 day divided by 30. The overall study BRV exposure duration (in

months) including Up-Titration Period (only DE subjects), Evaluation Period and Down-Titration Period (only discontinued subjects) will be calculated as the date of the final dose of BRV in this study minus the date of the first dose of BRV in this study plus 1 day divided by 30.

Subject years of exposure are calculated as overall study BRV exposure duration (in months) multiplied by 30 divided by 360.

Both, the evaluation Period BRV exposure duration and the overall study BRV exposure duration will be summarized with quantitative descriptive statistics. The number and percentage of subjects with the following categories of Evaluation Period BRV exposure durations will also be presented: \leq 6 months, $>$ 6 to \leq 12 months, $>$ 12 to \leq 18 months, $>$ 18 to \leq 24 months, $>$ 24 to \leq 30 months, $>$ 30 to \leq 36 months, and $>$ 36 months.

The number and percentage of subjects exposed overall and by 6 month exposure durations (\leq 6 months of exposure, $>$ 6 months of exposure, $>$ 12 months of exposure, $>$ 18 months of exposure ...) will be presented overall and by modal dose category (see Section 3.2.8).

Additionally, the table will show mean subject years of exposure overall and by modal dose categories.

All BRV exposure data will be listed.

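### Section 3.2.3 gives completers who stop BRV no workable Down-Titration or Safety Period, so their time after the Final Visit is missing from by-period outputs only

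*SAP*

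**What the plan says.** The design text gives completers a taper. Section 2.3.1 says that "for subjects who complete the study but do not continue BRV treatment, the Down-Titration Period starts with scheduled Down-Titration Visits", then allows at most 4 weeks of taper followed by 2 drug-free weeks and the Safety Visit. Table 3-1 carries conditional marks for the DTV and SV in both the DE and LTFU rows, separate from the row for early discontinuations. Its footnote makes those marks depend on what the subject does after the FV.

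The derivation rules in Section 3.2.3 read differently:

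- Evaluation Period end, completer: "If the subject continues the study until it ends, the Evaluation Period ends on the date of FV".
- Evaluation Period end, discontinuer: "If the subject prematurely discontinues the study, the date of EDV is the end date".
- Down-Titration, who is covered: "A discontinued subject or a subject who completes the study but does not continue BRV treatment".
- Down-Titration, entry: the subject counts as "entering the Down-Titration Period only if the subject has a record of at least 1 dose of BRV after the date of EDV".
- Down-Titration, start: "The start date of the Down-Titration Period is set as 1 day after the date of EDV".
- Safety Period, entry: "A discontinued subject is considered to have entered the Safety Period if the subject has at least 1 contact" after the final dose. It starts the day after that dose.

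Section 8.1, listing what overall exposure includes, adds "Down-Titration Period (only discontinued subjects)".

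**The concern.** Section 3.2.3 treats the FV and the EDV as alternative ends of the Evaluation Period, yet the next rule relies on the EDV alone. A completer who tapers therefore cannot meet the entry condition, and the start date is undefined. The Safety Period sentence does not mention completers at all. Section 8.1 contradicts Section 2.3.1, Table 3-1 and the Down-Titration rule's own subject clause.

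Withdrawal is the phase these two periods exist to describe. If completers' days there have no period, the Down-Titration and Safety columns describe discontinued subjects only, who are a selected group. Two programmers could also build different by-period tables of TEAEs, a primary variable, from the same text.

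**Working it through.** The SAP states no figure on this point to reproduce. The check applies the Section 3.2.3 rules day by day.

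**Inputs.** Taper of w weeks, w = 1 to 4 (maximum 4, Section 2.3.1). Drug-free time of 2 weeks = 14 days (same section). Assumed for the check: the FV (or EDV) falls on day F, the last dose on day F + 7w, and the Safety Visit on day F + 7w + 14.

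**Days to be assigned after F:** 7w + 14, that is 21, 28, 35 or 42.

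**Rules applied.**
1. Evaluation: up to day F.
2. Down-Titration: needs an EDV and a dose after it; runs from EDV + 1 to the last dose.
3. Safety: needs a discontinued subject with a contact after the last dose; runs from last dose + 1 to last contact.

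| Reading | Down-Titration days | Safety days | Unassigned days (w = 1, 2, 3, 4) |
|---|---|---|---|
| Completer, literal text | 0 | 0 | 21, 28, 35, 42 |
| Completer, EDV read as FV or EDV | 7w | 0 | 14, 14, 14, 14 |
| Discontinued subject, same dates, literal text | 7w | 14 | 0 |
| Completer, Down-Titration and Safety rules both repaired | 7w | 14 | 0 |

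For w = 4, the literal text leaves 28 + 14 = 42 days without a period, and the repaired text gives 28 Down-Titration and 14 Safety days.

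**Is there a fallback?** Section 3.2.3.1 ranks the periods when a partial date fits more than one. It does not place an event that fits none.

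**Outputs that use these periods.**
- TEAE incidence by study period (Section 8.2.2).
- Laboratory PCST for the Safety Period, and for Evaluation and Safety combined (Section 8.3).
- The number entering Down-Titration (Section 5.1).
- Down-Titration incidence of new seizure types (Section 3.10.3.1).
- Attribution of procedures, consultations, hospital stays and ER visits to periods (Sections 3.10.4.2 to 3.10.4.5).

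**Outputs that do not.**
- Overall TEAE tables: the definition in Section 3.10.1 has no end date.
- Overall exposure: the formula in Section 8.1 runs to the final dose in the study.
- Vital-sign and laboratory summaries by visit label (Sections 8.3 and 8.4.1).
- Listings.

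**The case against.** The best defence is that EDV is shorthand for FV or EDV. Table 3-1 heads the last Evaluation column with both visits, Section 3.10.3.1 says they share one eCRF page, and the Down-Titration rule would not name completers if it meant to exclude them. This is a fair guess at the intent for Down-Titration. It does not repair the Safety Period sentence, which is limited by type of subject and not by visit, and Section 8.1 still conflicts.

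A reader might infer more than the SAP supports:

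- *That completers' withdrawal events disappear from safety reporting.* They do not. They remain in the overall, serious, drug-related and intensity TEAE tables and in the listings.
- *That tapering completers belong to no period at all.* They are in the Evaluation Period up to the FV. Only later days are affected.
- *That exposure is counted without its events.* Overall exposure and overall TEAEs both include the taper. Section 8.2.2 bases percentages on subjects at risk, and no exposure-adjusted rate by period is planned. The exposure formula gives the same value with or without the parenthesis in Section 8.1.
- *That hospital-stay tables are distorted.* Section 3.10.4.4 derives sums by period, but Section 9.3.4 plans tables by 6-month interval and exposure cohort, not by period.

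The affected group may also be small. Several ends of participation in Section 2.3.3, such as approval, managed access or transfer to another BRV study, point to continued BRV, for which the Table 3-1 footnote drops the DTV and SV.

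**Conclusion.** The concern holds in limited form. The SAP contradicts itself on whether completers who stop BRV have Down-Titration and Safety Periods, and its rules cannot place their time after the FV. The size per affected subject is at most 42 days on the literal text. With the generous reading of EDV, 14 drug-free days remain, assuming the Safety Visit falls 2 weeks after the last dose. Ten such completers would account for at most 10 × 6 = 60 subject-weeks; the actual number is not given.

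The consequence is incomplete by-period output, including one planned table of a primary variable. Overall safety conclusions are not changed, and no hypothesis test is involved. The point concerns analysis periods only and says nothing about how BRV should be tapered.

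**What to change.** Make three wording changes before database lock:

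1. Section 3.2.3, Down-Titration: replace *EDV* with *FV or EDV* in both the entry condition and the start-date rule.
2. Section 3.2.3, Safety Period: extend entry to completers who do not continue BRV and have a contact after the final dose. Leave the rule for discontinued subjects as it stands. A condition about moving to marketed BRV or another BRV study must not be applied to them, because the present text has none and they would lose a period they now have.
3. Section 8.1: replace the restriction to discontinued subjects with *subjects who enter Down-Titration*.

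The cost is a short SAP amendment and one change to the period derivation in the analysis dataset. No new data are needed.

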3.2.3.1 Assignment of safety variables to study periods

In general, safety variables (e.g. AEs) will be allocated to the treatment group based on the dose most recently received. Safety outcomes which can be classified into more than 1 study period as per Section 3.2.3, based on partial dates of onset, will be classified into a study period based on the following prioritization: Up-Titration, Evaluation, Down-Titration, Safety, (for example, an AE that can be classified in both the Evaluation and Safety Period based on a partial date of onset due to a missing day entry, will be classified into the Evaluation Period).

3.2.4 Monthly time intervals

A month is defined as 30 days and time intervals based on monthly durations are defined as a multiple of 30 days (eg, 12 months is defined as 360 days). The definitions of 3- and 6-month

intervals are based on the durations in [Table 3–2](#), which use 30-day months where EV relative days as defined in Section [3.2.1.2](#) will be used:

Table 3–2: Definition of monthly interval durations during the first year

Interval	EV relative days
Months 1 to 3	1 to 90
Months 4 to 6	91 to 180
Months 7 to 9	181 to 270
Months 10 to 12	271 to 360
Months 1 to 6	1 to 180
Months 7 to 12	181 to 360

Subsequent 3 and 6-month intervals, and 12-month intervals are defined in a similar manner.

Three-month intervals will be calculated for summaries and analyses of efficacy and safety outcomes scheduled to be assessed at each MEV, FEV, YEV and FV. A subject is included in the analysis for a 3-month interval if the end of their evaluation period is on or after the final day of the 3-month interval and the seizure diary was completed for at least 1 day during the 3-month interval.

Six-month intervals will be calculated for summaries and analyses of efficacy and safety outcomes scheduled to be assessed at each FEV, YEV and FV, but not each MEV. Similar to the approach for inclusion in 3-month summaries detailed above, a subject is included in the analysis for 6-month intervals if the end of their evaluation period is on or after the final day of the 6-month interval and the seizure diary was completed for at least 1 day during the 6-month interval.

Six and 12-month intervals will be calculated for analyses of seizure freedom. For further information on subject inclusion into these calculations, see Section [3.10.3.1](#).

For the analysis of AEs, a subject is included in the analysis for a 3-month interval if the end of their evaluation period is on or after the first day of the 3-month interval.

3.2.5 Study visit labeling

Visits will be labeled in table summaries (according to the schedule outlined in [Table 2–1](#)) as follows:

- “Screening Visit”
- “Up-Titration Visit X”
- “Entry Visit”
- “Month X” for scheduled visits during the Evaluation Period
- “Final Visit”
- “Early Discontinuation Visit”
- “Down-Titration Visit”

- “Safety Visit”
- “Last Value” (see below in Section 3.2.6 for further information)

Listings will also include “Unscheduled Visit” as applicable.

3.2.6 Last Value on BRV treatment

The Last Value on BRV treatment for all assessments is the final available result obtained after the first dose of BRV and prior to or on the date of the final dose of BRV within evaluation period. All scheduled and UV assessments within evaluation period will be considered. Last Value will be determined separately for each vital sign, ECG and laboratory parameter.

3.2.7 Exposure duration and exposure duration cohorts

The overall duration of exposure for each subject will be calculated as the date of the final dose of BRV minus the date of the first dose of BRV plus 1 day.

Each subject will be classified into 1 or more of the following exposure duration cohorts based on the duration of BRV exposure as calculated above:

Table 3–3: Exposure duration cohort definitions

Cohort	Definition
All subjects	≥ 1 day
> 3 months	> 90 days
> 6 months	> 180 days
> 9 months	> 270 days
> 12 months	> 360 days

This categorization will continue in 3-month increments past 12 months up to a time point that will be determined based on a review of cumulative exposure on the database performed prior to database lock (DBL).

3.2.8 Modal dose calculation

Modal daily doses will be calculated across all study days on or after the day of first dose of BRV and up to and including the day of last dose of BRV. Modal daily dose is the most frequently taken daily dose during this period. In the event of a tie, the modal dose will be set to the lower of the tied doses. Modal daily dose will be categorized as follows:

Table 3–4: Dose group definitions for calculation of modal dose

Dose group label (mg/kg/day)
>=0.0 to <1.0
1.0 to < 2.0
2.0 to < 3.0
3.0 to < 4.0
>=4.0

For each subject, the mode will then be calculated and they will be assigned to one of the groups in [Table 3-4](#) overall, and by 6-month cohort.

3.2.9 Mapping of assessments performed at Early Discontinuation Visit

Efficacy and safety assessments at an EDV that correspond to a scheduled visit will be summarized at the scheduled visit corresponding to the EDV if the assessment was scheduled to occur at that visit. Such assessments will also be considered for Last Value on BRV treatment (see Section [3.2.6](#)).

In particular, clinical laboratory parameters, vital signs, and body weight are assessed at all Evaluation Period visits, and so all assessments of these variables at EDVs corresponding to a scheduled visit will be mapped to the corresponding scheduled visit.

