2.3.1 Study design for DE subjects

The screening period comprises the screening visit (ScrV).

Directly enrolled subjects will begin receiving BRV in the Up-Titration Period at Titration Visit 1 (TV1) after all inclusion and exclusion criteria are met. The BRV dose will be titrated to optimize tolerability and seizure control. Subjects may enter the Evaluation Period after they have remained on the same daily dose (no lower than the minimum specified dose) for 7 ± 2 days that, in the opinion of the Investigator, has demonstrated acceptable tolerability and seizure control. Up to 3 TVs may be needed before entry into the Evaluation Period.

Evaluation Period starts with the Entry Visit (EV) followed by Minimal Evaluation Visits (MEV), Full Evaluation Visits (FEV), Yearly Evaluation Visits (YEV), possibly Unscheduled Visits (UV) and Early Discontinuation Visits (EDV), if applicable. For more detailed information of visits scheduled, see [Table 2-1](#)

Table 2-1: Visit sequence

DE subjects		
	Visit	Type of visit
	ScrV	Screening
W1	TV1 ^a	TV
W2	TV2 ^a	TV
W3	TV3 ^a	TV

All subjects		
First year follow-up		
M0	V1	EV ^b
M1	V2	MEV
M2	V3	FEV
M3	V4	MEV ^c
M4	-	-
M5	-	-

M6	V5	FEV
M7	-	-
M8	-	-
M9	V6	MEV ^c
M10	-	-
M11	-	-
Second and subsequent years follow-up^d		
M12	V7	YEV
M15	V8	MEV
M18	V9	FEV
M21	V10	MEV
and every 3 months thereafter	V11, V12, etc.	YEV, MEV, etc.

BRV=brivaracetam; EV=Entry Visit; FEV=Full Evaluation Visit; LTFU=long-term follow-up; M=Month; MEV=Minimal Evaluation Visit; ScrV=Screening Visit; TV=Titration Visit; V=Visit; W=Week; YEV=Yearly Evaluation Visit

Note: Visits at W1, W2, W3, and M0 will occur 7 ± 2 days after the previous visit; visits at M1, M2, and M3 will occur 30 ± 7 days after the previous visit; visits at M6, M9, M12, M15, M18, M21 and every 3 months thereafter will occur 90 ± 15 days after the previous visit.

“-” denotes that no visit is scheduled in that month.

^a All DE subjects must participate in at least TV1, but may participate in fewer than 3 TVs as described in Section 7.2.1 of the protocol.

^b For LTFU subjects, the EV is the final evaluation visit of the core study. For DE subjects, the EV represents the point of entry into the Evaluation Period.

^c Hepatic monitoring tests only will be performed as described in Section 9.5.1 of the protocol.

^d Subsequent years will follow the same visit schedule.

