8.3 Clinical laboratory evaluations

Clinical laboratory results will be summarized using conventional units. Observed values and change from Baseline values for hematology, biochemistry (including hepatic monitoring of ALT, AST, ALP, total bilirubin, and GGT) and endocrinology parameters will be summarized for Baseline, each scheduled visit in the Evaluation Period, Last Value on Treatment, and the Safety Visit (if available). These summaries will be repeated separately for data collected during the Up-Titration visits for DE subjects.

Presentation of urinalysis results will consider subjects by age group for whom sample collection is feasible due to the constraints on collection for subjects below 4 years of age in the protocol. Following age groups will be presented: ≥ 4 to < 12 years, ≥ 12 years to < 17 years and overall.

In microscopic urinalysis, a small sample of urine is centrifuged to remove the liquid. The sediment is then examined under a microscope. In the urinalysis laboratory test group, other than qualitative responses, a listing of microscopic analysis parameters will be provided; no summaries of microscopic analysis findings are planned.

Response categories are negative, 1+, 2+, and 3+ for the quantitative urinalysis parameters occult blood, leukocytes, glucose, protein, and ketones and negative and positive for nitrates. Outcome values for these parameters are mapped to the levels Negative, 1+, 2+, and 3+ as follows for purposes of summary tables and the determination of PCST:

Table 8-1: Urinalysis categorization

Category	Definition
Negative	“Negative”, “NEGATIVE” or other outcomes that clearly reflect a negative finding
1+	“1+”, “+”, “Trace”, “TRACE” or other outcomes that clearly reflect trace amount
2+	“2+” or “++”
3+	“3+”, “+++” or other outcomes that clearly reflect the data above 3+ (eg, “4+”, “5+” etc.) or more than 4 plus signs (eg, “++++”, “+++++” etc.)

For qualitative urinalysis parameters (occult blood, leukocytes, glucose, protein, ketones, and nitrates), the number and percentage of subjects with each response category will be summarized for Baseline, EV, each scheduled visit during the Evaluation Period for which urinalysis parameters were scheduled to be assessed, Last Value on Treatment, and the Safety Visit. Percentages for each parameter will be relative to the number of subjects with a microscopic urinalysis assessment at each time point. The summary will be repeated for the Up-Titration period for DE subjects.

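### The EDV mapping rule in SAP Section 3.2.9 sends non-hepatic laboratory values to Months 3 and 9, where Table 2-1 schedules hepatic tests only

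*SAP*

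**What the plan says.** Section 3.2.9 has two paragraphs. The first gives a general condition: an EDV assessment "will be summarized at the scheduled visit corresponding to the EDV if the assessment was scheduled to occur at that visit". The second applies it to three groups of variables. It asserts that "clinical laboratory parameters, vital signs, and body weight are assessed at all Evaluation Period visits, and so all assessments of these variables at EDVs" are carried over; in full, the consequence reads "so all assessments of these variables at EDVs corresponding to a scheduled visit will be mapped to the corresponding scheduled visit". No exception is made by parameter or by visit.

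Table 2-1 in Section 2.3.1 marks the Month 3 visit (V4) and the Month 9 visit (V6) with footnote c: "Hepatic monitoring tests only will be performed as described in Section 9.5.1 of the protocol". Section 8.3 shows that the hepatic panel is only part of one laboratory group: "biochemistry (including hepatic monitoring of ALT, AST, ALP, total bilirubin, and GGT".

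For hematology, biochemistry and endocrinology, Section 8.3 plans observed values and changes that "will be summarized for Baseline, each scheduled visit in the Evaluation Period, Last Value on Treatment, and the Safety Visit (if available". It also keeps unscheduled visits out of those tables. Urinalysis is worded more narrowly, at "each scheduled visit during the Evaluation Period for which urinalysis parameters were scheduled to be assessed".

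**The concern.** The second paragraph of 3.2.9 rests on a premise that Table 2-1 contradicts, and it leads to a mapping that the first paragraph does not allow. A programmer who follows the specific sentence fills the non-hepatic rows at Months 3 and 9. One who follows the general sentence leaves them empty. The SAP supports both readings.

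If the rows are filled, they do not describe the same population as the rows around them. Children who continue have no scheduled hematology, endocrinology or non-hepatic chemistry at those visits, so the values come from children at the point of leaving the study. A difference in mean or median from neighbouring visits could then reflect who left rather than time on treatment.

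**Working it through.** No figure in the plan needs to be reproduced. The check sets the provisions side by side and counts visits.

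**Step 1. Is the premise true at every visit?** The visits after entry through Month 12 in Table 2-1 are:

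| Visit | Month | Type | Footnote c (hepatic only) |
|---|---|---|---|
| V2 | 1 | MEV | no |
| V3 | 2 | FEV | no |
| V4 | 3 | MEV | yes |
| V5 | 6 | FEV | no |
| V6 | 9 | MEV | yes |
| V7 | 12 | YEV | no |

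The premise fails at 2 of 6 visits for hematology, endocrinology and all biochemistry other than ALT, AST, ALP, total bilirubin and GGT. For vital signs it agrees with Section 8.4.1, which lists MEV, FEV and YEV. The fault lies in the laboratory clause.

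**Step 2. Do the two paragraphs of 3.2.9 give the same result?** Take a hematology result from an EDV that corresponds to Month 3.

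- First paragraph: hematology was not due at Month 3, so the result is not mapped and the cell stays empty.
- Second paragraph: hematology is a laboratory parameter, so the result is mapped and the cell is filled.

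The results differ.

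**Step 3. Which planned outputs are reached?**

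- Observed-value and change tables for hematology, biochemistry and endocrinology: Section 8.3 calls for every scheduled Evaluation Period visit, so Months 3 and 9 are included. Unscheduled results are excluded and continuing children have no scheduled non-hepatic collection. Mapped EDV values are therefore the only planned source.
- Urinalysis summaries: limited in Section 8.3 to visits at which urinalysis was due, so not affected.
- PCST counts: specified for the Evaluation and Safety Periods, separately and combined. A period-level count does not depend on the visit label.
- Last Value (Section 3.2.6): the final on-treatment result within the Evaluation Period, whatever its visit label. Not affected.

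**Step 4. What about later years?** Months 15 and 21 in Table 2-1 carry no footnote c, yet footnote d says that later years repeat the same schedule. Through Month 36 the post-entry visits are Months 1, 2, 3, 6, 9, 12, 15, 18, 21, 24, 27, 30, 33 and 36, which is 14. If footnote c applies only where it is printed, 2 of 14 are hepatic-only. If it recurs at the corresponding visits (Months 15, 21, 27 and 33), 2 + 4 = 6 of 14 are.

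**The case against.** The best defence is that the governing rule is already correct. The first paragraph of 3.2.9 carries the right restriction, and the second opens as an illustration of it. Read parameter by parameter, the first paragraph gives empty cells and no distortion. It is also fair to say that hepatic tests are laboratory parameters and are done at Months 3 and 9, so the sentence is loose at panel level rather than wholly wrong. This explains how the text arose but does not settle it: the second paragraph is the only sentence that deals with laboratory data by name, and it says that all such values are mapped.

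The points about importance stand. The primary variables are treatment-emergent AEs and SAEs (Section 2.2.1), laboratory tests are among the other variables (Section 2.2.3), and every summary is descriptive (Section 3.1). Each continuous summary shows n, so a sparse row would be visible to a careful reader.

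A reader might infer that every non-hepatic laboratory summary at Months 3 and 9 is affected, or that the primary safety results are distorted. The SAP supports neither: urinalysis is protected by its own wording, period-level PCST counts and Last Value do not use the mapping, and the primary variables are untouched. Even in the affected rows, the word exclusively would be too strong, because a test done off schedule at a Month 3 or Month 9 visit could also appear.

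**Conclusion.** The laboratory clause in the second paragraph of 3.2.9 is wrong as written. It conflicts with footnote c of Table 2-1 and with the section's own first paragraph. Followed literally, it fills the Month 3 and Month 9 rows of the by-visit observed-value and change tables for hematology, endocrinology and non-hepatic biochemistry essentially with early discontinuers' values.

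The size is 2 of 6 post-entry visits in the first year, and 2 to 6 of 14 through Month 36 depending on how footnotes c and d are reconciled. The number of children in those rows cannot be calculated. The SAP gives no discontinuation rate, and 3.2.9 sets no window for deciding which scheduled visit an EDV corresponds to. It would be tempting to claim visible swings in the laboratory time course, but the documents give no data from which to show them.

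The conclusion assumes that the programmer follows the specific sentence over the general one and that footnote c reflects the protocol schedule to which it refers. The change should be made before the tables are programmed, but it concerns descriptive visit-level output and not the study's main conclusions.

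**What to change.** In the second paragraph of 3.2.9, either delete the reference to clinical laboratory parameters, so that the first paragraph governs them, or add that the mapping applies only where the parameter in question is scheduled. Either way, EDV laboratory values are mapped parameter by parameter. At Months 3 and 9 only ALT, AST, ALP, total bilirubin and GGT would be mapped.

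Other EDV laboratory values stay in the listings and in Last Value where they meet the Section 3.2.6 definition. A separate EDV row in the laboratory tables is optional. Section 3.2.5 already has the label, but Section 8.3 would need a matching line, as Section 8.4.1 has for vital signs.

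Reconcile footnotes c and d of Table 2-1 with the protocol schedule, so that it is clear whether hepatic-only testing recurs at the corresponding visits after year 1, and apply the same parameter-by-visit rule there.

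The cost is one sentence in 3.2.9, a footnote clarification and a parameter-by-visit lookup in programming. No data collection changes.
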